- Spain – Information System for Research in Primary Care (SIDIAP) as primary care databases

Hospital:

- Hospital de Madrid Hospitales

Data analysis

Continuous variables will be described using mean, standard deviation, median, first and third quartiles, minimum, and maximum. Categorical variables will be described by the number and percentage of patients in each category. Patterns of missingness will be reported and 95% confidence Intervals will be presented. The

results for each country and where available, each setting will be presented separately.

Primary Objective:

- Descriptive analysis for systemic glucocorticoid use patterns will be carried and stratified by setting, glucocorticoid exposure type (naive, prevalent) and subgroups of special interest.
- Kaplan-Meier methods will be used to estimate time to systemic glucocorticoid initiation from COVID-19 diagnosis, stratified by route of administration (oral vs intravenous).

Secondary Objective 1:

- Cohort-specific descriptive statistics summarizing demographic, health and clinical patient characteristics, stratified by setting, glucocorticoid exposure type glucocorticoid (naive, prevalent), and subgroups of special interest will be presented.

Secondary Objectives 2 and 3:

- Crude incidence (presented as both proportions and rates) for the relevant outcomes for each of the treatment exposure groups will be calculated.
- The cumulative incidence rates will be reported at the end of follow-up (30 and 90 days).
- Data will be stratified by setting, glucocorticoid exposure type (naive, prevalent), and subgroups of special interest
- Cox regression models (using multivariable models and using PS adjustment) will be used to compute the adjusted incidence rates.

Secondary Objective 4:

- The performance of different COVID-19 disease definitions based on rule-based phenotype algorithms will be explored using diagnostic predictive modelling

**Plans for
Disseminating
and
Communicating
Study Results**

IQVIA will produce a study report in accordance with the GVP guidelines VIII (EMA/813938/2011). Study information (including protocol and final report) will be added in the EU PAS register.

Section 3.0 Amendments and Updates

Major and Minor Amendments	
Major Amendments	Minor Amendments

 None 	
 Abstract section Appendix 3 Misspellings and editorial checks across the entire document

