7.2.3 Follow-up

Two index date definitions will be applied as appropriate for each objective.

- Diagnosis index date is defined as a positive PCR test for SARS-CoV-2 (labCOVID-19) or a confirmed COVID-19 diagnosis(diagCOVID-19) whichever is the earliest.
- Treatment index date is defined as start of first systemic glucocorticoid treatment episode specifically for the treatment of COVID-19, irrespective of whether the patient is a prevalent or naïve user.

Follow up for all patients will begin from the index date until they experience the outcome of interest (endpoint, depending on the objective) or until cohort exit (date of censoring). The patients will be followed up for maximum 90 days or until censoring occurs, censoring criteria are:

- death
- patient exit (deregister) from a contributing data provider (GP practice)
- end of the database's data collection
- end of study period (latest data cut-off)

The lookback window for evaluating risk factors, medical history is 365 days and will be applied only to outpatient cohorts.

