Only the first episode of exposure will be considered, patients being censored when they switch to another treatment (including switch to another glucocorticoid) or when follow up ends. Duration of follow-up for each treatment cohort will be summarized and will constitute the denominator for calculation of effect estimates. A persistence window of 7 days between drug utilization records for each study drug will be allowed considered as continuous exposure for the outcome's assessment.

In case that more than 70% of the patients are censored, a sensitivity approach will be applied for objectives 2 and 3 (see Section 7.7.8).

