7.7.3 Patient characteristics (secondary objective 1)

Summary descriptive statistics will be presented by the four cohorts (section 7.2.2) and *described both at diagnosis and treatment index dates in each cohort*. The following will be described at diagnosis date and also treatment index date: patient demographics and clinical characteristics. Where available, a description of COVID-19 illness onset (time to diagnosis), associated symptoms and time to hospitalization for COVID-19 infection will be presented.

Data will be further stratified by subgroups of special interest (see section 7.2.4).

7.7.4 Estimation of incidence of study adverse events of interest and disease outcomes (secondary objectives 2 and 3)

The crude incidence rate of the individual outcome relevant to each sub-cohort reported during person-time treated for each exposure group will be calculated. The crude person-time from relevant index date will be calculated for the following groups:

- Use of systemic glucocorticoids without other treatments for COVID-19 (drug and respiratory support)
- Use of systemic glucocorticoids plus other treatments for COVID-19 (drug and respiratory support)
- Only other treatments and respiratory support with no steroids
- No specific treatments for COVID-19 infection (other concomitant treatments are allowed are allowed)

Only the earliest eligible treatment is considered, and for patients who switch to another treatment (including switch to another glucocorticoid), their follow-up is censored at date of switching. The number and reasons for patients censoring will be reported.

We will calculate both, the incidence proportion and the incidence rate. The numerator for both (risk and rate) will be comprised of counts of incident events of interest during the person-time as defined above recorded during each cumulative interval and summed to reflect the cumulative count for the interval.

The crude cumulative incidence rate will be calculated according to the formula:

$$\frac{\text{Total number of patients on Rx with first event during cumulative interval of interest}}{\text{Total person-time at risk (days)}} \times 100$$

The crude incidence proportion will be calculated according to the formula:

$$\frac{\text{Total number of patients on Rx with first event during cumulative interval of interest}}{\text{Total population at risk at start of study period}} \times 100$$

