For each sub-cohort and type of person-time the numerator for each time frame will contain the number of patients for whom an outcome has been recorded in that time frame since the onset of that type of person-time. The crude incidence rate of each outcome within the relevant sub-cohort will be expressed as number of cases per 1,000 patient-days at risk.

The cumulative incidence rate will be reported at the end of follow-up (30 and 90 days).

The person-time estimation and the calculation of the crude incidence rate for secondary objectives 2 and 3 will be similar except for the outcomes being considered in each case. For secondary objective 2, adverse events of interest for glucocorticoids (listed in Section 7.3.3) will be the outcome, and for secondary objective 3 mortality and other disease outcomes (Section 7.3.4) will be the outcome.

Both stratification and adjustment will be used as a method to deal with confounders.

In order to examine risk factors of the outcomes of interest, data will also be stratified by subgroups of interest (7.2.4) and stratum-specific crude incidence rates will be calculated. The stratification variables include the healthcare setting, glucocorticoid user type (naive, prevalent) treatment groups and subgroups of special interest.

Separate Cox regression models will be used to estimate adjusted cause-specific HR³ (in order to account for competing events) for each outcome **within** the following four treatment groups:

- Use of systemic glucocorticoids without other treatments for COVID-19 (drug and respiratory support)
- Use of systemic glucocorticoids plus other treatments for COVID-19 (drug and respiratory support)
- Only other treatments and respiratory support with no systemic glucocorticoids

³ Cause-specific HR are to be interpreted as instantaneous risk estimates and not as cumulative risk estimates; cumulative risks estimates are subject to competing events <https://pubmed.ncbi.nlm.nih.gov/30012114/>

- No specific treatments for COVID-19 infection (other concomitant treatments for indications other than for COVID-19 are allowed)

In addition to stratified analysis, for each of the above four treatment groups, two sets of Cox regression models will be run:

- 1) A model that is adjusted for a list of predefined confounders
- 2) A model that is adjusted for a high dimension propensity score that is derived through large-scale modelling, using all available covariates in each dataset (Section 7.7.5)

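### One average crude rate over days 0-30 and 0-90, for groups and databases with unequal observed time, is not comparable across them if the hazard falls after the acute phase

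*Protocol*

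**What the plan says.** Section 7.7.4 defines the measure: "The crude incidence rate of the individual outcome relevant to each sub-cohort reported during person-time treated for each exposure group will be calculated". The numerator is first events, "recorded during each cumulative interval and summed to reflect the cumulative count for the interval". The result "will be expressed as number of cases per 1,000 patient-days at risk". On timing, the section says "The cumulative incidence rate will be reported at the end of follow-up (30 and 90 days", and the abstract (Section 2.0) repeats this: "The cumulative incidence rates will be reported at the end of follow-up (30 and 90 days". Only these two cumulative windows are named; no separate window after day 30 is defined.

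The rates are produced for four groups: glucocorticoids alone, glucocorticoids plus other treatments, other treatments only, and no specific treatment.

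On follow-up, Section 7.2.3 says "The patients will be followed up for maximum 90 days or until censoring occurs". Its censoring list contains death, leaving the data provider, end of data collection and end of study, but not end of treatment. Section 7.3.2.3 adds censoring at a switch and a 7-day persistence window, and says "Duration of follow-up for each treatment cohort will be summarized and will constitute the denominator for calculation of effect estimates". Section 7.7.8 offers a sensitivity analysis that uses all observed person-time regardless of treatment, and contrasts this with treated person-time. Table 1 puts the data locks at April 2020 for HM Hospitales, June 2020 for UK IMRD, November 2020 for LPD France and December 2020 for the other five.

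**The concern.** Events divided by person-time give a weighted average of the hazard over the days that happen to be observed. That average describes a group without distortion only if the hazard is constant, or if every group is observed over the same days. The outcomes here are acute: admission, intensive services, thromboembolism, infection and death after an acute illness. A hazard that falls with time is plausible for many of them. A group seen mainly in its first days then shows a higher rate than one followed to day 90, even when the two share the same hazard.

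At stake is how the tables are read. A higher 0-90 day rate for a short-observed group or an early-locked database could be taken as a difference in risk. Section 7.9.1 warns about confounding by severity but does not mention this artefact.

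**Working it through.** **No figure to reproduce.** The protocol states no rate, person-time or hazard for this point. The check applies its own rate definition to assumed hazards.

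**Inputs from the protocol**
- Windows of 30 and 90 days, first events only, scale per 1,000 patient-days (7.7.4). The displayed formula multiplies by 100 instead; this does not affect ratios.
- Maximum follow-up 90 days (7.2.3).
- Persistence window 7 days (7.3.2.3).
- A course of at most 10 days is cited in 7.3.2.3. It is used only to illustrate treated time: 10 days, or 10 + 7 = 17 with the window.
- Lock months from Table 1, taken generously as the last day of the month.

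**Step 1: data locks, independent of treatment**
- HM Hospitales: 31 January 2020 + 90 days = 30 April 2020. No patient indexed after 31 January can reach day 90. A patient indexed on 1 March has at most 60 days.
- UK IMRD: 1 April 2020 + 90 days = 30 June 2020. No patient indexed after 1 April can reach day 90.

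HM Hospitales is the only hospital source (7.5), so the hospital 0-90 day rate is weighted to early days.

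**Step 2: end of treatment, where the text conflicts**

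| Person-time stops at end of treatment | Person-time runs on |
|---|---|
| 7.7.4 counts treated person-time | 7.2.3 omits end of treatment from its censoring list |
| 7.7.8 contrasts treated with all observed person-time | 7.3.2.3 names only a switch or end of follow-up |
| 7.3.2.3 sets a 7-day persistence window | |

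On the left-hand reading a short course contributes about 10 to 17 days, while the untreated group can contribute 90. On the right-hand reading this source of imbalance disappears for patients who do not switch.

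**Step 3: size under an assumed hazard**

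Rate(T) = 1000 × (1 − S(T)) / ∫₀ᵀ S(t) dt, with the same hazard in every group.

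Example: 5 per 1,000 days to day 14, then 0.5.
- S(14) = exp(−0.070) = 0.9324; person-days 13.52.
- T = 17: S = 0.9310; person-days 16.32; rate 4.23.
- T = 30: S = 0.9250; person-days 28.38; rate 2.64.
- T = 90: S = 0.8976; person-days 83.05; rate 1.23.

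| Observed to | Against full 30 days | Against full 90 days |
|---|---|---|
| 10 days (rate 5.00) | 1.89 | 4.06 |
| 17 days (rate 4.23) | 1.60 | 3.43 |
| 30 days (rate 2.64) | 1.00 | 2.64 / 1.23 = 2.1 |

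The last row corresponds to truncation at day 30 by a data lock.

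Ranges for 10 or 17 days observed:

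| Assumed hazard | 30-day ratio | 90-day ratio |
|---|---|---|
| Constant | 1.00 | 1.00 |
| Piecewise: high for 10, 14 or 21 days, then lower by a factor of 2, 5 or 10 | 1.17-2.46 | 1.42-4.90 |
| Exponential decay, time constant 7, 14 or 30 days | 1.20-2.30 | 2.34-6.76 |

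**Step 4: do the planned outputs repair it?**
- The incidence proportion moves the other way: 6.90% at 17 days observed against 10.24% at 90 days in the example.
- The Cox models are fitted within each group, so they do not align time across groups.
- The follow-up summary and censoring counts disclose the imbalance but leave the rate unchanged.
- The sensitivity analysis starts only above 70% censoring, which 7.7.8 ties to switching. A short course does not trigger it, and using all observed person-time does not undo an early lock.

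**Step 5: separate windows.** In the example, the rates are 5.0 for days 0-7, 5.0 for days 8-14 and 0.5 thereafter, whoever is observed. The ratio is 1.00 in every shared window.

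**The case against.** The strongest reply is that no comparison is intended. Section 6.3 places comparative safety out of scope, Section 7.9.1 says no comparative analysis will be done, and results are presented separately by database. That lowers the weight of the point but does not remove it. The four groups share one scale, Section 7.7.8 refers to a reference group for these rates, and Section 7.9.1 justifies on-treatment exposure by comparability with trial results.

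Second, the hazards are assumed. This stands. The protocol gives no reason to expect a falling hazard for every listed outcome, for example hypertension, myopathy or psychosis.

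Third, much is already planned: proportions, time to onset, reasons for censoring, follow-up duration and cause-specific models. A reader with events and person-days for both windows could obtain days 31-90 by subtraction. These outputs help to detect the problem, but the rate fixed in 7.7.4 remains the average. Table layout can be left to an analysis plan; the choice of estimator is already made in the protocol.

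Fourth, databases locked in December also truncate patients diagnosed in the autumn. This is right: the contrast between databases depends on the calendar spread of diagnoses, which the protocol does not give. The only planned pooling (7.7.7) concerns hazard ratios at 30 days, not these crude rates.

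**Conclusion.** The point holds as a conditional one, and a change is advisable. If the hazard falls over time, the 0-90 day crude rate differs between groups with identical hazards by roughly 1.4 to 5-fold under the piecewise declines tried, and the 0-30 day rate by about 1.2 to 2.5-fold. If the hazard is constant there is no distortion. These sizes rest on assumed hazards and on 10 or 17 observed days.

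Two stronger conclusions that a reader might draw are not supported. One is that both windows are distorted several-fold: that size belongs to the 90-day rate, and only under the steeper declines. The other is that short glucocorticoid courses will necessarily produce a false safety signal: that needs person-time to stop at the end of treatment, which the protocol leaves contradictory, and a comparison that it disclaims. The data-lock part does not depend on how that conflict is resolved.

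**What to change.** In Section 7.7.4, with the abstract and Sections 7.2.3, 7.3.2.3 and 7.7.8 aligned:

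1. State whether person-time ends at the end of treatment, and reconcile the censoring lists accordingly.
2. Report events, person-days and rates in non-overlapping windows for each group and database: at minimum 0-30 and 31-90 days, with finer early windows where counts allow.
3. Print mean observed time beside any 0-90 day average, with a note that it is not comparable across groups or databases.
4. Add the cumulative incidence function, with death as a competing event for non-fatal outcomes, in databases that record death. Section 7.9.2 says DA Germany, LPD France and LPD Italy do not record vital status.

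The cost is wording and extra table columns from data that are extracted anyway. The drawback is sparse late windows for rare outcomes, above all in the single hospital database of around 2,000 patients.

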6.1 Aim

EMA wish to generate real world evidence to describe the utilisation patterns of systemic glucocorticoids in patients with COVID-19 and investigate the risks of adverse outcomes including non-fatal complications and deaths occurring within the first 6 months following COVID-19 diagnosis in patients treated with systemic glucocorticoids, as observed in ambulatory and hospital inpatient care settings of seven European countries during the first year of the pandemic until latest data availability.

6.2 Primary Objective

To describe utilization of systemic glucocorticoids (e.g., dexamethasone, prednisolone, methylprednisolone or hydrocortisone) for treatment of COVID-19 in two settings: hospitalized (in hospital care) and ambulatory (any care received outside of hospital) within 90 days following COVID-19 diagnosis. The following variables will be described:

- Prevalent use or naïve (incident) use of systemic glucocorticoid at date of diagnosis of COVID-19
- Concomitant use of other medications (number and type) and invasive/non-invasive respiratory support during follow up
- Type of systemic glucocorticoid received
- Time to systemic glucocorticoid initiation from COVID-19 diagnosis
- Route of administration
- Systemic glucocorticoid daily dose at initiation (treatment index date), cumulative duration, distribution of duration of use and cumulative dose of systemic glucocorticoid received
- For prevalent users: proximity of previous glucocorticoid use to COVID-19 diagnosis (current use (concomitant on date of COVID-19 diagnosis, recent use (between 15-30 days before date of COVID-19 diagnosis) or remote use (use ended more than 30 days before date of COVID-19 diagnosis))

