7.3.2 Exposures

The following exposures of interest are captured in this study

Table 2 Exposures of interest

	Cohort	When is measured
Glucocorticoids used in COVID-19 indication	All	At diagnosis index date and follow-up
Glucocorticoids for pre-existing conditions	Only in prevalent users' cohort	Before diagnosis index date
Other COVID-19 treatments: 
 • antiviral therapy (AV) • antibiotic therapy (AB) • immune-based therapy (IB) • antithrombotic therapy (AT) • anti-hypertensives (AH) • statins (S) • anti-diabetic (AD) (see Appendix 3)	All	At diagnosis index date and during follow-up
Oxygen therapies	All	At diagnosis index date and during follow-up*

* During follow-up this will be considered as an outcome

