7.3.2.1 Glucocorticoids

Glucocorticoids used in COVID-19 indication

The primary treatment group of interest is based on exposure to systemic glucocorticoids. The following drugs will be considered as being used for COVID-19 diagnosis:

- Dexamethasone (H02AB02)
- Prednisone (H02AB07)
- Prednisolone (H02AB06)
- Methylprednisolone (H02AB04)
- Hydrocortisone (H02AB09)

Only glucocorticoids which were investigated in clinical trials (13,21) or are recommended by clinical guidelines are included (22–24) to avoid misclassification of steroids used for other conditions. As indication is not captured in the available databases, a glucocorticoid treatment will be considered to have been initiated for COVID-19 treatment if:

For incident users

- The glucocorticoid treatment was initiated between 2 before and 30 days after COVID-19 diagnosis date (21)
- It is one of the five glucocorticoids recommended for COVID-19 as above

For prevalent users

- The glucocorticoid treatment was initiated between 2 before and 30 days after COVID-19 diagnosis date
- It is one of the five glucocorticoids recommended for COVID-19 as above
- The glucocorticoid started after COVID-19 diagnosis differs from the chronically used glucocorticoids OR there is a change in dose or schedule of administration compared to the prevalent use, occurred after COVID-19 diagnosis.

Glucocorticoids for pre-existing conditions

For the prevalent users, any steroid in the ATC class H02 glucocorticoids for systemic use will be considered. A patient is defined as a systemic glucocorticoids prevalent user if it has at least one prior exposure to systemic² glucocorticoids in the 120 days prior to diagnosis index date.

For the description of prevalent users of glucocorticoids, categories of use will be created based on proportion of days covered (PDC) during the lookback period. PDC is calculated as the number of days in period covered by prescriptions divided by number of days in the period.

- PDC > 85% as heavy user
- PDC 50-85% as moderate user
- less than 50% PDC as light user

Another categorization of prevalent glucocorticoids user will be based on how recently in the past the last prescription was observed:

- current use (concomitant on date of COVID-19 diagnosis)
- recent use (between 15-30 days before date of COVID-19 diagnosis)
- remote use (use ended more than 30 days before date of COVID-19 diagnosis)

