7.3.2.3 Operationalization of exposure metrics

Cumulative duration

For glucocorticoids used in COVID-19 indication

Exposure to a treatment will commence on the date of the first qualifying record, subject to satisfying all inclusion criteria listed in section 7.2.2. Each drug exposure record has a start date and inferred end date, which is either explicitly entered or derived from other available information, such as days' supply or refills. Duration of each episode will be calculated as end date minus start date or directly from days' supply variable, whatever available. For each patient, the cumulative duration of use will be calculated as the sum of the duration of treatment episodes.

Table 3 Calculation of duration of use and end of treatment across databases

	IPCI	UK IMRD	Germany DA	Belgium LPD	SIDIAP	France LPD
If days_supply is missing	Use amount and dose extracted from the sig	Use daily dosage along with prescribed quantity	Impute with the most frequent daily dosage or DDD at a therapy level	Use calculated quantity/units_per_day.	Use the quantity, daily dosage and DDD of each drug	Use the quantity and daily dosage of each drug
If still missing	Use the DDD and prescribed quantity	Impute most frequent daily dose at the drug level	-	-	-	-
If still missing	Use the modal duration in the database					

DDD= defined daily dose; sig - the directions ('signetur') on the drug prescription as recorded in the original prescription (and printed on the container) or dispensing record from the physician.

Daily dose

For glucocorticoids used in COVID-19 indication, the prescribed daily dose at initiation of glucocorticoid (treatment index date) will be recorded and categorized in low and high dose. The definition of low dose and high dose will use the cut off defined by WHO in their prospective meta-

analysis from REACT subgroup (16), namely: 15 mg/d of dexamethasone, 400 mg/d of hydrocortisone, and 1 mg/kg/d of methylprednisolone.

The current recommendation is to use 10 mg of dexamethasone for maximum 10 days, administered orally or intravenously. In case glucocorticoids other than dexamethasone are administered, their dose will be converted in prednisolone equivalents as described:

<https://emedicine.medscape.com/article/2172042-overview>

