Steroids often have adjusted dose regimens such that drug may be slowly increased or decreased over time and short acute treatment episodes are also possible. Such changes in dose over time will not be examined, however total cumulative dose will be examined in relation to outcomes of interest (see below).

Cumulative dose

For glucocorticoids used in COVID-19 indication, orally administered, if quantity is available, the formula to calculate the cumulative exposure in mg is described below:

$$Cumulative\ dose_{solid}[mg] = \sum_{all\ exposures} quantity \times amount_value [mg]$$

If the **quantity is missing**, the number of units per day for solid formulations are extracted. The cumulative exposure in mg can then be calculated using the following formula:

$$Cumulative\ dose_{solid}[mg] = \sum_{exposures} units\ per\ day \times amount_value [mg] \times duration$$

For intravenous administration (bolus administration), the dose administered each time will be counted.

$$Cumulative\ dose\ intravenous [mg] = \sum_{all\ exposures} amount_value [mg]$$

Exposure groups for incidence calculation (secondary objective 2 and 3)

For the incidence rates calculation, an on-treatment exposure will be considered with mutually exclusive groups to allow calculation of incidence rates.

Each person will be classified as belonging to one of the following mutually exclusive exposure groups at treatment index date following COVID-19 diagnosis:

- Use of systemic glucocorticoids without other treatments for COVID-19 (drug and respiratory support)
- Use of systemic glucocorticoids plus other treatments for COVID-19 (drug and respiratory support)
- Only other treatments and respiratory support with no systemic glucocorticoids

- No specific treatments for COVID-19 infection (other concomitant treatments for indications other than for COVID-19 are allowed)

A single prescription would be enough to consider the patient as exposed. See section 7.3.2.1 for description of 'other treatment for COVID-19' that are included.

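### For prevalent users still on treatment at diagnosis, the COVID-19 glucocorticoid dose includes the usual dose when that drug is changed but leaves it out when a second drug is added

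*Protocol*

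**What the plan says.** The primary objective (section 6.2) concerns systemic glucocorticoids given to treat COVID-19, and lists "Systemic glucocorticoid daily dose at initiation (treatment index date), cumulative duration, distribution of duration of use and cumulative dose of systemic glucocorticoid received" among the variables to be described.

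Table 2 in section 7.3.2 sets when each exposure is measured. COVID-19 glucocorticoids are measured "At diagnosis index date and follow-up". Glucocorticoids for pre-existing conditions, which apply to prevalent users only, are measured "Before diagnosis index date".

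Indication is not captured, so section 7.3.2.1 classifies a prevalent user's record as COVID-19 treatment by a rule on timing and drug, plus this condition: "The glucocorticoid started after COVID-19 diagnosis differs from the chronically used glucocorticoids OR there is a change in dose or schedule of administration". The second arm requires that "there is a change in dose or schedule of administration compared to the prevalent use, occurred after COVID-19 diagnosis".

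Section 7.3.2.3 then defines the doses.
- Dose per day: "For glucocorticoids used in COVID-19 indication, the prescribed daily dose at initiation of glucocorticoid (treatment index date) will be recorded". It is then classed as low or high.
- Accumulated amount: "For glucocorticoids used in COVID-19 indication, orally administered, if quantity is available, the formula to calculate the cumulative exposure in mg is described below". The formulas sum the qualifying records and have no term for the usual dose.
- Use of the result: "Such changes in dose over time will not be examined, however total cumulative dose will be examined in relation to outcomes of interest".

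Section 7.7.2 summarises these results by the four cohorts and by subgroup, without a split by qualifying route. Section 7.2.4 makes the starting dose, low or high, a stratifier for the primary objective and for secondary objectives 1 to 3.

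**The concern.** The two qualifying routes put different things into the same variable. If the usual drug's dose is changed, the changed prescription is the qualifying record, and it carries the maintenance part as well as whatever was added. If a different glucocorticoid is added, that drug alone qualifies. The usual drug, continuing unchanged, meets neither arm of the rule and has no measurement after diagnosis, so it drops out.

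Two prevalent users with the same intake can therefore have different recorded daily and cumulative doses. A mean or median dose in a prevalent-user cohort then depends partly on how many patients came in by each route. The low/high starting-dose subgroup and any description of outcomes by cumulative dose inherit the mix. The dose columns for naive and prevalent users also cannot be read side by side, because in naive users the recorded dose has no maintenance part.

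**Working it through.** The protocol states no dose distribution and no power figure that bears on this, so there is nothing to reproduce. The check applies the protocol's own rule and formulas to two prevalent users with identical intake.

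**Inputs.** All three are assumptions for illustration, in one common equivalent scale. They are not protocol figures and not recommended doses.
- b = usual dose, 5, 10 or 20 mg/day, continued through the course
- a = added dose, 40 mg/day (range 20 to 60)
- d = 10 days of COVID-19 course

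**Formulas, from sections 7.3.2.1 and 7.3.2.3**
- Usual drug changed: daily dose a + b, cumulative dose (a + b) × d
- Different drug added, usual drug continued: daily dose a, cumulative dose a × d
- Shortfall of the second record against the first: b / (a + b)

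**Results with a = 40, d = 10**

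| b | usual drug changed | different drug added | shortfall |
|---|---|---|---|
| 5 | 45 mg/day, 450 mg | 40 mg/day, 400 mg | 5/45 = 11.1% |
| 10 | 50 mg/day, 500 mg | 40 mg/day, 400 mg | 10/50 = 20.0% |
| 20 | 60 mg/day, 600 mg | 40 mg/day, 400 mg | 20/60 = 33.3% |

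Over a = 20 to 60 and b = 5 to 20, the shortfall runs from 5/65 = 7.7% to 20/40 = 50%.

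**Effect on a cohort mean.** Take a = 40, b = 10, d = 10 and let s be the share of affected patients on the changed-drug route. The mean recorded daily dose is 40 + 10s. It moves from 40 mg/day (400 mg) at s = 0 to 50 mg/day (500 mg) at s = 1, with no change in intake.

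**Low/high class.** Two patients with equal intake fall in different classes only when the cut-off lies between a and a + b. The documents do not show how often that would happen.

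**Duration.** In this example both routes count d days, so cumulative duration does not show the same mix.

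**Who is affected.** Section 7.3.2.1 makes a patient prevalent on a single exposure in the previous 120 days, and its recency categories include use that ended more than 30 days before diagnosis. The omission needs all three of the following: current use at diagnosis, a different glucocorticoid started, and the usual one continued. The documents do not size this group.

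**The case against.** The strongest reply is scope. The governing sentence of section 6.2 limits the listed variables to treatment of COVID-19. Sections 7.1, 7.2.3 and 7.3.2.3 keep to that limit. On this reading, leaving out an unchanged maintenance drug is intended. That stands, and a reader who infers that the objective promises total systemic glucocorticoid burden goes further than the text. But the same reading then counts against the other route, where the maintenance part is counted. The rule also admits any change, so a reduced dose of the usual drug qualifies and contributes its whole remaining amount. Whichever quantity is meant, one route does not deliver it.

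A reader might also infer that more than half of 90-day exposure is lost. With U for the usual dose, 90U/(90U + 400) does give 53% to 82% for U = 5 to 20. That figure is not the size of this problem, because most of it is maintenance use outside the 10-day course. If the patient on the changed-drug route returns to the usual dose, that use is no longer a qualifying change and is left out too: 80U/(90U + 400) = 47% to 73%. The gap between routes is 10U/(90U + 400), or 5.9 to 9.1 percentage points of 90-day intake.

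Three further limits stand. If the new drug replaces the old one, its record is already the full intake. A same-drug top-up prescription would be an increment, and the protocol does not say how to tell it from a full new dose. Section 7.2.4 makes the subgroups descriptive only, and background use is described separately by days covered and recency. This last point gives context but does not separate the two quantities within the dose results.

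Handling of overlapping records could be left to the SAP. Here, though, the protocol itself fixes the measurement window, the classification rule and the formulas, and an SAP that follows them reproduces the mix.

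**Conclusion.** The point holds for a defined group: prevalent users who are current users at diagnosis. Among them, daily and cumulative dose is a total on one qualifying route and only the added drug on the other when the usual drug continues. On the assumed figures, equal intake is recorded 11% to 33% lower on the added-drug route during the course. This assumes that a changed prescription states the full new dose. Users whose earlier treatment has ended and naive users are unaffected, and no dose is omitted when the new drug replaces the old.

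It is worth correcting because the values are primary-objective results and also define a subgroup. It does not undermine the naive-user cohorts, and its effect on the prevalent-user cohorts depends on a group whose size the documents do not give.

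**What to change.** - In section 7.3.2.3, state one quantity for both qualifying routes: either the total systemic dose or the increment over the pre-diagnosis dose. Use the same quantity for the low/high subgroup. Section 7.3.2.1 already needs the earlier dose to detect a change, so the increment asks for little that is new.
- In Table 2, extend the row for pre-existing glucocorticoids to follow-up, so that continuation and replacement can be told apart in the ambulatory databases. Either quantity needs this.
- In section 7.7.2, report prevalent-user doses separately for patients whose usual drug was changed and patients who started a different drug.

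The cost is some wording and extra programming. Continuation must be inferred from recorded supply, so some error remains. Sections 7.4 and 7.9.2 say that only SIDIAP links primary and secondary care and that medical history is limited in the hospital setting. Usual primary-care use will mostly be unseen in the hospital database, and there only the route split with a stated caveat is realistic.
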